4.3 Immunotherapy

Immunotherapy will be delivered in the form of PD-1/PD-L1 blockade using approved anti PD-1/PD-L1 agents. Dose reductions are appropriate for toxicity as specified or at the discretion of the treating medical oncologist. Prior immunotherapy as part of multi-drug therapy or monotherapy is acceptable prior to initiation of SBRT.

The DLT observation period for continuation or discontinuation of therapy is defined as 14 days starting with cycle 1, day 1. To be evaluable for DLT, a patient must have received at least the first 2 administrations and be monitored for at least 14 days following the first administration. Any of the below outlined events occurring during each DLT observation period and considered to be at least possibly related to Nivolumab will qualify as a DLT.

Non-Hematologic Toxicity

1. Grade ≥ 2 uveitis
2. Any Grade ≥ 3 non-hematologic toxicity except
 - a. Nausea, vomiting or diarrhea
 - b. Clinically insignificant laboratory abnormalities
 - c. Grade 3 infusion reactions that respond to medical management
 - d. Grade 3 immune related effects other than uveitis that improve within 7-14 days with steroid treatment (Appendix 1).

Hematologic Toxicity

1. Grade 4 neutropenia lasting more than 1 week
2. Grade 4 thrombocytopenia
3. Grade 3 thrombocytopenia with bleeding
4. Grade ≥ 3 febrile neutropenia

Special

1. Grade ≥ 2 pneumonitis

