7. IMMUNOTHERAPY

Immunotherapy administration will commence or continue following the conclusion of SBRT/SABR.

Immunotherapy will be administered as an IV infusion as specified. It is not to be administered as an IV push or bolus injection. At the end of the infusion the administration line will be flushed with a sufficient quantity of normal saline per standard of care. Infusions will continue on a standard schedule for the specific immunotherapy agent with pre-treatment assessments for adverse effects using a standard questionnaire.

Immunotherapy administration will be delayed in the case of any of the following:

Any Grade ≥ 2 non-skin, drug-related adverse event, with the following exceptions:— Grade 2 drug-related fatigue or laboratory abnormalities do not require a treatment delay

Any Grade 3 skin, drug-related adverse event

Any Grade 3 drug-related laboratory abnormality, with the following exceptions for lymphopenia, leukopenia, AST, ALT, or total bilirubin:

- Grade 3 lymphopenia or leukopenia does not require dose delay
- If a subject has a baseline AST, ALT or total bilirubin that is within normal limits, delay dosing for drug-related Grade ≥ 2 toxicity
- If a subject has baseline AST, ALT, or total bilirubin within the Grade 1 toxicity range, delay dosing for drug-related Grade ≥ 3 toxicity

Any adverse event, laboratory abnormality, or intercurrent illness which, in the judgment of the investigator, warrants delaying immunotherapy administration.

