Eye event: Uveitis (iritis, iridocyclitis)	Grade 1	Discontinue IMMUNOTHERAPY if symptoms persist despite treatment with topical immunosuppressive therapy	
 • Evaluation by an ophthalmologist is strongly recommended. • Treat with topical steroids such as 1% prednisolone acetate suspension and iridocyclitics. 	Symptoms may include (but are not limited to): 
 • Blurred vision • Diffuse erythema and a prominent blush on the sclerae • Dryness of the eyes • Pain • Photophobia 	All attempts should be made to rule out other causes such as metastatic disease, infection, or other ocular disease (e.g., glaucoma or cataracts).
	Grade 2	Discontinue IMMUNOTHERAPY if symptoms persist despite treatment with topical immunosuppressive therapy and do not improve to Grade 1 within the retreatment period OR requires systemic treatment.	
 • Evaluation by an ophthalmologist is strongly recommended. • Treat with topical steroids such as 1% prednisolone acetate suspension and iridocyclitics. 		
	Grade 3-4	Discontinue IMMUNOTHERAPY.	
 • Treat with systemic corticosteroids such as prednisone at a dose of 1-2 mg/kg per day. When symptoms improve to \leq Grade 1, steroid taper should be started and continued over no less than 4 weeks. 		

Event(s)	CTCAE v4.03 Grade	Management	Action/Supportive Care Guidelines	Symptoms ^a	Differential Diagnosis
Hepatic events 
 Hepatitis Hepatitis, Autoimmune 	Grade 1-2	Withhold IMMUNOTHERAPY if there is a treatment-emergent concurrent elevation of ALT and bilirubin that corresponds to an upward shift of 2 or more grades in both parameters.	
 Monitor liver function tests more frequently until returned to baseline values. 	Symptoms may include (but are not limited to): 
 Elevations in: 
 AST >2.5 ULN ALT >2.5 ULN Total bilirubin >1.5 × ULN 	All attempts should be made to rule out other causes such as metastatic disease, progressive liver disease, viral hepatitis,

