Event(s)	v4.03 Grade	Action/Supportive Care Guidelines	Symptoms	Diagnosis
Renal events	Grade 1	
 Consider withholding IMMUNOTHERAPY if event does not improve with symptomatic treatment 	
 Provide symptomatic treatment. Monitor creatinine weekly; when it returns to baseline, resume routine creatinine monitoring per protocol. 	
All attempts should be made to rule out other causes such as obstructive uropathy, progression of disease, or injury to other chemotherapy agents. A renal consultation is recommended.

	Grade 2	
 Consider withholding IMMUNOTHERAPY. 	
 Systemic corticosteroids at a dose of 1-2 mg/kg/day of prednisone or equivalent may be indicated. When symptoms improve to Grade 1 or less, corticosteroid taper should be started and continued over at least 1 month. Consider prophylactic antibiotics for opportunistic infections. Consider renal biopsy. If elevations persist >7 days or worsen, treat as Grade 4. 	
Renal failure, Acute	Grade 3-4	
 Discontinue IMMUNOTHERAPY. 	
 Renal consultation with consideration of ultrasound and/or biopsy as appropriate. Monitor creatinine daily. Treat with systemic corticosteroids at a dose of 1-2 mg/kg prednisone or equivalent once per day. When symptoms improve to grade 1 or less, steroid taper should be started and continued over no less than 4 weeks. Discontinue IMMUNOTHERAPY if unable to reduce corticosteroid dose for irAEs to ≤10 mg. IMMUNOTHERAPY treatment may be restarted and the dose modified as specified in the protocol. 	
 Symptoms may include (but not limited to): Fatigue High blood pressure Increased serum creatinine Swelling

CTCAE Management/

Symptoms^a

Differential

Event(s)	v4.03 Grade		Action/Supportive Care Guidelines	Diagnosis

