Skin events 
 • Dermatitis • exfoliative Erythema • multiforme Stevens-Johnson syndrome Toxic epidermal necrolysis 	Grade 1-2	No change in dose	Symptomatic treatment should be given such as topical glucocorticosteroids (eg, betamethasone 0.1% cream or hydrocortisone 1%) or urea-containing creams in combination with oral antipruritics (eg, diphenhydramine HCl or hydroxyzine HCl). Treatment with oral steroids is at investigator discretion for Grade 2 events.	All attempts should be made to rule out other causes such as metastatic disease, infection, or allergic dermatitis.
	Grade 3	Hold IMMUNOTHERAPY.	Consider dermatology consultation and biopsy for confirmation of diagnosis. 
 • Treatment with oral steroids is recommended, starting with 1 mg/kg prednisone or equivalent once per day or dexamethasone 4 mg four times orally daily. When symptoms improve to Grade 1 or less, steroid taper should be started and continued over no less than 4 weeks. 	
	Grade 4	Permanently discontinue IMMUNOTHERAPY.	Dermatology consultation and consideration of biopsy and clinical dermatology photograph. Initiate steroids at 1-2 mg/kg prednisone or equivalent. When symptoms improve to grade 1 or less, steroid taper should be started and continued over no less than 4 weeks.	
If considered to be immune related, ≥ Grade 3 or result in dose modification or discontinuation: 
 • Pruritus • Rash • Rash generalized • Rash maculo-papular • Vitiligo 	≤ Grade 1	No change in dose		
	Grade 2	No change in dose		
	Grade 3	No change in dose	Grade 3 drug-related thrombocytopenia >7 days or associated with bleeding requires discontinuation.	
	Grade 4	Hold IMMUNOTHERAPY until resolves to ≤ Grade 1. May increase the dosing interval by 1 week.	Grade 4 drug-related thrombocytopenia >7 days or associated with bleeding requires discontinuation.	
Thrombocytopenia				

^a The signs and symptoms may be associated with any of the diagnoses in the associated "Event(s)" column.

^b REMICADE (Infliximab) prescribing information

^c If symptoms indicate possible new or worsening cardiac abnormalities, additional testing and/or a cardiology consultation should be considered.

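### DLT evaluability requires two doses even for a patient whose DLT after the first dose ends treatment, and only nivolumab-related events can be DLTs

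*Protocol*

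**What the plan says.** Protocol section 4.3 sets the window: "The DLT observation period for continuation or discontinuation of therapy is defined as 14 days starting with cycle 1, day 1". It then sets the condition for being counted: "To be evaluable for DLT, a patient must have received at least the first 2 administrations and be monitored for at least 14 days" after the first dose. The two requirements are joined by *and*. Neither this section nor any other offers an alternative route for a patient who has already had a DLT.

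The events that count are described as "Any of the below outlined events occurring during each DLT observation period and considered to be at least possibly related to Nivolumab". The list that follows includes Grade 2 or higher uveitis, most Grade 3 or higher non-hematologic toxicity, certain cytopenias and, under a separate heading, Grade 2 or higher pneumonitis. One exemption covers "Grade 3 immune related effects other than uveitis that improve within 7-14 days with steroid treatment".

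The same section allows any approved anti-PD-1/PD-L1 agent. Section 2.1 and Study Addendum 1 name both nivolumab and pembrolizumab. Section 7 covers patients new to immunotherapy as well as those already on it: "Immunotherapy administration will commence or continue following the conclusion of SBRT/SABR".

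**The concern.** An evaluability rule should remove patients who were not observed well enough to show whether they had the event. It should not remove patients because they had it. A patient whose toxicity after dose 1 permanently ends immunotherapy cannot satisfy a two-dose requirement, so the rule discards some of the most serious DLTs. It keeps milder ones, such as Grade 2 pneumonitis that resolves and allows re-dosing.

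The attribution wording is a separate fault. If only nivolumab-related events qualify, no event in a patient on pembrolizumab can be a DLT, although that patient receives protocol treatment.

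Both faults make the combination look better tolerated than it is. Section 3.1 makes safety, feasibility and tolerability of the sequential combination the primary objective of the pilot phase, so a DLT count reported from it should not depend on either.

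**Working it through.** The protocol gives no DLT rate, DLT threshold or number of DLT-evaluable patients, so there is no figure to reproduce. The check is one of timing and wording, followed by an illustration.

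**Timing.** The window is days 1 to 14 from the first dose. Section 2.0 cites nivolumab every 2 weeks, so dose 2 is due on day 1 + 14 = 15. Study Addendum 1 cites pembrolizumab every 3 weeks, so dose 2 is due on day 1 + 21 = 22. On either schedule dose 2 comes after the window has closed. The second dose adds no exposure within the window and in effect requires that the patient was fit to be re-dosed. The phrase *each DLT observation period* hints at later windows, but none is defined.

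**Which listed DLTs end treatment (Appendix I).**
- Grade 3-4 pneumonitis: discontinue. Pneumonitis is listed as a DLT in its own right at Grade 2 or higher, so the steroid-response exemption to the general Grade 3 item does not remove it.
- Grade 3-4 uveitis: discontinue. For Grade 2 uveitis: "Discontinue IMMUNOTHERAPY if symptoms persist despite treatment with topical immunosuppressive therapy and do not improve to Grade 1 within the retreatment period".
- Thrombocytopenia: "Grade 3 drug-related thrombocytopenia >7 days or associated with bleeding requires discontinuation". The same condition applies at Grade 4. The DLT list includes Grade 3 with bleeding and all Grade 4.
- Grade 4 skin events: permanently discontinue.

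**Which patients are not lost.**
- Grade 2 pneumonitis is held and may resume, so dose 2 can still be given.
- For Grade 3-4 renal events the table also says "IMMUNOTHERAPY treatment may be restarted and the dose modified as specified in the protocol".
- Grade 3 immune-related events covered by the steroid-response exemption are not DLTs.
- Events that only delay dose 2 cause no loss.
- For patients continuing immunotherapy, the first two administrations may already have been given.

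The loss is therefore confined to new starters with a treatment-ending DLT after dose 1.

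**Illustration, part 1 (all inputs assumed).** Let q be the true DLT rate and f the share of DLT patients never re-dosed, with all other patients evaluable. A fraction qf of patients drops out of both numerator and denominator:

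reported rate = q(1 − f) / (1 − qf)

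| True q | f = 25% | f = 50% |
|---|---|---|
| 5% | 3.8% | 2.6% |
| 10% | 7.7% | 5.3% |
| 20% | 15.8% | 11.1% |
| 30% | 24.3% | 17.6% |

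For q = 10% and f = 50%: 0.10 × 0.50 / (1 − 0.05) = 0.05 / 0.95 = 5.3%. In 20 patients this means 1/19 instead of 2/20. At f = 0 there is no bias. f cannot exceed the share of DLT patients who are new starters.

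The expected number lost in 20 patients is 20qf. This is 20 × 0.05 × 0.25 = 0.25 patients at q = 5%, f = 25%, and 20 × 0.10 × 0.50 = 1 patient at q = 10%, f = 50%.

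**Illustration, part 2 (literal reading, inputs assumed).** If a share p of patients receives pembrolizumab and the DLT rate is the same on both agents, the reported rate is q(1 − p). With q = 10% it is 7.5%, 5.0% and 2.5% at p = 25%, 50% and 75%.

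**What depends on these rules.** Section 3.1 evaluates the first 20 patients for 15 weeks and restricts lung-directed therapy if more than 5% have Grade 3 or higher pneumonitis. In 20 patients that means 2 or more, since 1/20 is exactly 5%. Neither step mentions DLT evaluability or attribution to nivolumab. The adverse event visits in Appendix III (30 days after SBRT, then every 3 months) do not either.

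**The case against.** The strongest reply is that nothing in the protocol uses a DLT rate. Section 4.3 ties the period to continuing or stopping therapy, which reads as a rule for the individual patient. The objectives, the design section and the planned analyses mention no DLT cohort, threshold or summary. A new starter with Grade 3-4 pneumonitis after dose 1 still counts toward the pilot's only numerical rule, and under section 5.4 is asked to attend the remaining visits. This stands, and it is why the point is minor. It does not remove the fault: an evaluability criterion mainly serves to decide who is counted, and this one is stated wrongly rather than left open.

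Second, the size is not anchored. The protocol's one timing figure, a median of 15 weeks to onset of treatment-related pulmonary events on nivolumab alone, suggests that few such events would fall within 14 days, although SBRT could shorten this. This also stands, and the percentages above are hypothetical.

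Third, the nivolumab wording looks like a leftover that sites would read sensibly. Probably so, but it is current text and contradicts the opening of its own section.

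A reader might also infer that the window must start at the first SBRT fraction and that events due to SBRT alone must count as DLTs. The documents do not support calling their absence an error. Section 4.3 governs the drug, at-least-possible relatedness already captures overlapping toxicity, and SBRT follow-up is handled separately. Those would be design preferences.

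**Conclusion.** The point holds as a minor wording fault with two parts. The two-dose condition makes a new starter non-evaluable because of the outcome when a DLT after dose 1 permanently ends immunotherapy. The nivolumab-only attribution, taken literally, means that no event in a pembrolizumab patient can be a DLT. Both push any DLT count among evaluable patients downward.

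The first part rests on the dosing intervals that the protocol cites and on the stopping rules in Appendix I. Its size depends on the DLT rate, the share of DLT patients never re-dosed and the mix of new and continuing patients, none of which the protocol gives. It could be zero.

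A reader might infer that the pilot's safety decision is compromised. It is not: the 15-week evaluation, the pneumonitis rule and adverse event reporting do not depend on DLT evaluability. Nor is every early DLT lost, since many allow re-dosing and continuing patients may already meet the condition.

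**What to change.** Make two edits in section 4.3.

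1. Evaluability: *A patient is evaluable for DLT who either had a DLT after any administration in the observation period, or received the first two administrations and was followed for 14 days or longer from the first.*
2. Attribution: replace nivolumab with *the study PD-1/PD-L1 agent, alone or in combination with SBRT*.

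With the first edit no patient is lost for having had a DLT. In the example above the count returns to 2/20 = 10%. The two-dose requirement for event-free patients and the start of the window stay as they are.

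The cost is a change of wording. The one downside for the sponsor is that the reported DLT rate may be slightly less favourable.

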2.0 PROPOSED TRIAL RATIONALE

Anti-PD-1 antibodies have demonstrated activity in the treatment of lung cancer. Opdivo was approved in February of 2015 by the FDA for patients with metastatic squamous NSCLC with progression on or after platinum based therapy. In the open-label trial, patients were randomized to receive OPDIVO (n=135) administered at 3mg/kg every 2 weeks. Median survival was improved to 9.2 months compared to 6 months in patients receiving docetaxel (n=137) 75mg/m² every 3 weeks, p=0.00025. Median progression free survival was slightly improved to 3.5 months compared to 2.8 months but 1 year overall survival was improved to 42% compared to 24% (36).

We expect that improvements in local control, increased immunogenic response and abscopal effect seen with combined modality treatment will result in improved local control, progression free survival and resultant significant increases in overall survival beyond 3 months. We propose a pilot/phase II study to assess the safety and efficacy of combination immunotherapy and stereotactic ablative radiation therapy (I-SABR).

Treatment will be a sequential combination treatment of SABR/SBRT and immunotherapy to assess the safety and feasibility of treatment. SABR/SBRT will be administered in 3-5 daily treatments followed by immunotherapy following the conclusion of SABR/SBRT. This approach will take advantage of the transient increase in antigen availability, increased antigen presentation and upregulation of PD-1 by tumor cells following ablative radiation therapy. After an interim safety analysis, the study will continue to the phase II portion where overall survival, progression free survival and response rate will be the primary and secondary end points. For reference, outcomes will be compared to the immunotherapy arms of checkmate 057 and Keynote 042 trials.

Several trials examining combination I-SABR are currently underway. A table of selected studies is included in [Table 1](#).

Study (Institution)	SABR Target	Dose (Gy/Fractionation)	Immunotherapy Agent	Sequence
NCT02239900 (MD Anderson Cancer Center)	Liver Lung Adrenal	50/4 60/10	Ipilimumab	Concurrent/Sequential
NCT01862900 (Chiles Research Institute)	Lung Liver	15/1 201/1	Anti-OX40	Concurrent
NCT01769222 (Stanford University)	Any	20/2	Ipilimumab	Concurrent
NCT02298946 (NIH/NCI)	Liver	8/1 24/3	PD-1 Inhibitor	Sequential

Table 1. List of selected ongoing I-SABR studies

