Since the development of this study, additional data regarding immunotherapy has emerged. Additional immunotherapy agents have shown efficacy in the treatment of metastatic NSCLC in the first line setting. Pembrolizumab is a humanized monoclonal antibody against the PD-1 with antitumor activity in advanced NSCLC expressing PD-L1. The Keynote-024 trial compared previously untreated advanced NSCLC with PD-L1 expression on at least 50% of tumor cells and no sensitizing mutation of the epidermal growth factor receptor gene or translocation of the anaplastic lymphoma kinase gene to receive either Pembrolizumab (at a fixed dose of 200 mg every 3 weeks) or the investigator's choice of platinum-based chemotherapy (1). Median progression free survival, 6 month overall survival and response rate were significantly improved in the Pembrolizumab arm. Pembrolizumab has now redefined initial systemic therapy for PD-L1 expressing tumors in the metastatic setting.

We hereby propose that immunotherapy in this trial now include Nivolumab or Pembrolizumab as long as patients are eligible.

References

1. Reck M et al. *N Engl J Med.* 2016 Nov 10;375(19):1823-1833. Epub 2016 Oct 8.

STUDY ADDENDUM 2.

Since the last re-authorization of the study, there have been several changes in the immunotherapy landscape from randomized phase III trials. These changes affect our proposed utilization of stereotactic body radiation therapy (SBRT) and immunotherapy in 17-009.

First line systemic therapy for metastatic lung adenocarcinoma now includes combination chemotherapy and immunotherapy. Keynote-189 showed an improved overall survival with pembrolizumab/alimta and carboplatin vs carboplatin/alimta alone (1). This survival benefit was higher with increasing PD-L1 expression but was maintained regardless of PD-L1 expression. Similarly, Key-407 showed an improved overall survival in patients with metastatic squamous cell lung carcinoma with combination carboplatin/taxol/pembrolizumab vs carboplatin/taxol alone (2) with PD-L1 expression $\geq 1\%$. Additionally, the PACIFIC trial showed an significant increase in overall survival in patients with stage III non-small cell carcinoma when Darvalumab was added following concurrent chemoradiation vs observation (3).

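### Section 4.3 requires two doses for DLT evaluability and makes no exception for a patient with a DLT, so a newly starting patient stopped for one would drop out of a DLT rate among evaluable patients

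*Protocol*

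**What the plan says.** All of the DLT rules are in Protocol section 4.3.

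- **Window:** "The DLT observation period for continuation or discontinuation of therapy is defined as 14 days starting with cycle 1, day 1".
- **Evaluability:** "To be evaluable for DLT, a patient must have received at least the first 2 administrations and be monitored for at least 14 days", the 14 days running from the first dose. Both conditions must be met.
- **Classification:** the next sentence covers any listed event in the period "considered to be at least possibly related to Nivolumab will qualify as a DLT". It does not say whether that patient is evaluable.

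The schedules come from elsewhere. Section 2.0 describes nivolumab "administered at 3mg/kg every 2 weeks", Study Addendum 1 describes pembrolizumab "at a fixed dose of 200 mg every 3 weeks", and section 2.1 allows either drug at its approved dosing. Section 7 adds: "Immunotherapy administration will commence or continue following the conclusion of SBRT/SABR". Some patients therefore start immunotherapy on study and others continue it.

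After toxicity, section 7 states: "Immunotherapy administration will be delayed in the case of any of the following", and the list covers most Grade 2 or higher non-skin drug-related events. Appendix I goes further for some events. For Grade 3-4 pneumonitis and Grade 3-4 uveitis the instruction is "Discontinue IMMUNOTHERAPY". It also requires stopping for Grade 3 thrombocytopenia with bleeding and for Grade 4 skin events.

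**The concern.** An evaluability rule normally keeps patients who had too little exposure, or too little follow-up, from being called free of DLTs. A patient who has already had a DLT is informative whatever the exposure, so such rules usually let that patient in. Section 4.3 does not. Because dose 2 comes after the window, evaluability depends on what happens after the event. A patient with Grade 2 pneumonitis who recovers and resumes under Appendix I receives dose 2 and is evaluable. A patient with Grade 3 pneumonitis is stopped and is not. The DLTs that end treatment are the ones removed, so the error runs in one direction.

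Section 3.1 makes safety, feasibility and tolerability the pilot's primary objective, and section 4.3 holds the protocol's only DLT definition. What is at stake is a DLT summary for that objective which would look better than the experience it describes.

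**Working it through.** The protocol states no DLT rate, DLT threshold or DLT-based sample size, so there is no figure to reproduce. The check is a timeline, followed by an illustration.

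**1. When dose 2 falls.** Day of dose 2 = 1 + dosing interval; the window is days 1 to 14.

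| Schedule | Interval | Day of dose 2 | Days after day 14 |
|---|---|---|---|
| Nivolumab, every 2 weeks (section 2.0) | 14 | 1 + 14 = 15 | 1 |
| Pembrolizumab, every 3 weeks (Study Addendum 1) | 21 | 1 + 21 = 22 | 8 |

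These are the intervals the protocol cites; a longer one would only move dose 2 later. If the window is read as 14 elapsed days, nivolumab dose 2 coincides with its end, but a patient stopped during the window still never receives it.

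**2. What happens to a newly starting patient with a DLT in the window.** The patient has had one dose.

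| Event, a DLT under section 4.3 | Appendix I action | Dose 2 given? | Evaluable? |
|---|---|---|---|
| Pneumonitis, Grade 2, recovers and resumes | Hold, may resume | Yes | Yes |
| Pneumonitis, Grade 3-4 | Discontinue | No | No |
| Uveitis, Grade 3-4 | Discontinue | No | No |
| Thrombocytopenia, Grade 3 with bleeding | Discontinue | No | No |
| Skin event, Grade 4 | Permanently discontinue | No | No |

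**3. Illustration by count.** Assumptions: all 20 pilot patients are newly starting; k of them have a DLT in the window and never receive dose 2; nobody else has a DLT. As written the rate is 0/(20 − k). Counting every DLT it is k/20. Limits are exact (Clopper-Pearson) 95% limits.

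| k | As written | Upper limit | All DLTs counted | Upper limit |
|---|---|---|---|---|
| 1 | 0/19 = 0% | 17.6% | 1/20 = 5% | 24.9% |
| 2 | 0/18 = 0% | 18.5% | 2/20 = 10% | 31.7% |
| 3 | 0/17 = 0% | 19.5% | 3/20 = 15% | 37.9% |

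**4. Illustration by rate.** Let p be the true DLT rate and f the share of DLT patients stopped before dose 2, both assumed. The expected proportion among evaluable patients is p(1 − f)/(1 − pf).

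| p | f = 50% | f = 75% | f = 100% |
|---|---|---|---|
| 10% | 0.05/0.95 = 5.3% | 0.025/0.925 = 2.7% | 0% |
| 20% | 0.10/0.90 = 11.1% | 0.05/0.85 = 5.9% | 0% |

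The rate is understated whenever f is above zero.

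**The case against.** The strongest reply is that the biased quantity does not appear in the protocol. Section 4.3 ties the window to continuing or stopping therapy, which is a matter of managing one patient. No threshold or denominator is stated in terms of DLTs. The pilot rule in section 3.1 uses Grade 3 or higher pneumonitis in the first 20 patients, with no evaluability condition. All of this is correct, and it limits the weight of the point. It does not remove it: a rule on who is evaluable for DLT plays no part in treating an individual, and its only use is to decide who enters a summary.

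A second reply is that the classification sentence is unconditional, so the evaluability rule may be meant only to say who can be declared free of DLTs. That may well be the intention. But the sentence classifies an event; it does not make the patient evaluable. At best the two sentences pull against each other, and a reader might wrongly infer the stronger claim that such a DLT is not counted at all. The text supports less: the event is a DLT, but the patient falls outside a rate calculated among evaluable patients.

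A third reply concerns size. Section 3.1 cites pneumonitis in 5% of nivolumab patients in an earlier trial, with a median onset of pulmonary events at 15 weeks (105 days, against a 14-day window). Losing 1 to 3 of 20 patients therefore looks high for pneumonitis alone. Treating all 20 as newly starting is also generous, since continuing patients are admitted. This stands, so the figures show direction and mechanism and are not a forecast.

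**Conclusion.** The point holds in limited form. For patients newly starting immunotherapy, section 4.3 as written makes those discontinued for a DLT in the window non-evaluable, in tension with its own next sentence. A DLT rate among evaluable patients would be biased toward safety. Under the assumed 1 to 3 losses among 20 patients, it would read 0% instead of 5% to 15%. The documents supply neither a DLT rate nor the share of patients stopped, so the actual size is unknown and may be small.

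A reader might infer that the pilot's go-ahead is compromised. The documents do not support that: the only numerical rule is more than 5% with Grade 3 or higher pneumonitis, it does not use the DLT count, and the events are still collected as adverse events. Nor does the conclusion extend to patients continuing earlier immunotherapy, for whom section 4.3 does not say which doses are the first two.

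This is a drafting fault in a rule that serves the primary safety objective. It is worth correcting because the correction is so cheap.

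**What to change.** In section 4.3 replace the evaluability sentence with: *A patient is DLT-evaluable if they have a DLT in the observation period after any dose, or if they received the first 2 administrations and completed 14 days of monitoring after the first without a DLT.* In the sentence that follows, replace *Nivolumab* with *the study immunotherapy*, since section 2.1 also allows pembrolizumab.

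Leave the exemption for Grade 3 immune-related effects that improve on steroids (non-hematologic item 2d) as it is. It may seem natural to restrict it to patients who resume treatment, because Appendix I discontinues drug for some Grade 3 hepatic events. But that would again make counting depend on re-dosing.

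The cost is one sentence and one term. There are no new data or visits, and no treatment instruction or decision rule changes. The reported DLT rate may be slightly higher.
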